Nineteen out of 325 offspring (5.9%) with increased genetic risk according to the criteria used in the Pilot-2 trial tested positive for at least one autoantibody by the age of 2.4 years in the German BABYDIAB study (107). Seventeen of these 19 subjects (89%) developed multiple autoantibodies during prospective observation. Assuming a constant increase in autoantibody frequency from age 2 to

age 6 years, the expected cumulative incidence of at least one antibody would be 14.8% and that of at least two antibodies 13.0% by the age of 6, which is well within the 95% CI of the observed frequency of 20.7% of multiple autoantibodies in the young DiMe siblings.

The cumulative incidence of at least one autoantibody by the age of 4 years was 10.6% in siblings and offspring of affected subjects in the DAISY study from Denver (108). The frequency reached 37.9% in those carrying the DR3/4, DQB1*0302 combination. Published data are not available allowing an estimation of the frequency of at least one or at least two autoantibodies in subjects with increased genetic risk as defined in the Pilot-2 trial. Nevertheless a constant increase in the frequency of at least one autoantibody from age 4 to age 6 years, would result in an autoantibody prevalence of 15.9% by the age of 6 years in siblings and offspring irrespective of HLA-defined genetic risk. The DiMe study was used for the power calculation as it includes the largest long term follow-up of young relatives.

The estimation that 2032 infants should be randomized for the trial (Table 1) is based on the following assumptions:

1. a confidence level of 95%;
2. a statistical power of 80%;
3. a reduction of 40% in the hazard rate of type 1 diabetes in the intervention group;
4. a drop-out rate of 20%; and
5. a frequency of 10% of exclusive breast feeding (BF) up to the age of 6 months

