These figures represent a conservative estimate, since they are based on the lower 95% CI (7.6%) of the observed cumulative incidence of type 1 diabetes by the age of 10 years (15.4%) in young siblings with moderate (DQB1*0302/x) and slightly increased genetic risk (DQB1*02/y), and since the high risk (DQB1*02/0302) group was not considered in the calculations. In the Pilot-2 trial the prevalence of the high risk genotype (DQB1*02/0302) was about two times higher (absolute frequency 20%) among siblings of affected children than among offspring of affected parents. If also the young siblings carrying the high risk genotype in the DiMe Study should be included in the group at risk, the lower 95% CI would be 10.6%, which should result in a recommendation of 1920 infants to be randomized for the trial. However, fewer data from non-Finnish populations are available, explaining the caution of this sample size estimate.

Table 1. Estimation of the sample size for the trial

Assumptions:									
• Confidence level:	95%								
• Power:	80%								
• Reduction in the annual frequency of multiple auto-antibodies (≥ 2 AB) by the age of 6 years	30, 40 or 50%								
• Reduction in the annual frequency of type 1 diabetes by the age of 10 years	30, 40 or 50%								

Frequency of ≥ 2 AB by the age of 6	SAMPLE SIZE								
	30% effect			40% effect			50% effect		
	I	II	III	I	II	III	I	II	III
20.7% (*02 and/or *0302)	1048	1132	1165	558	602	626	338	364	382
18.5% (*0302/x, *02/y)	1196	1294	1330	636	688	716	386	418	438
9.9% (lower 95% CI)	2252	2438	2511	1200	1300	1334	732	792	832

Frequency of type 1 diabetes by the age of 10	SAMPLE SIZE								
	30% effect			40% effect			50% effect		
	I	II	III	I	II	III	I	II	III
18.3% (*02 and/or *0302)	1330	1492	1536	706	794	824	428	482	502
15.4% (*0302/x, *02/y)	1548	1782	1834	844	948	986	512	576	606
7.6% (lower 95% CI)	3250	3658	3768	1735	1952	2032	1056	1190	1250

Column I: Mathematical sample size
Column II: Sample size corrected for a drop-out rate of 20%
Column III: Sample size corrected in addition for a 10% frequency of exclusive BF up to the age of 6 months.

RECOMMENDATION: 2032 infants and families
SCREENING TARGET: 4516 infants

[figure not shown]

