All statistical analyses will be based upon the total cohort of subjects randomized into the trial. Although data on some subjects may be missing at points in time, all relevant data available from each subject will be employed in the analyses. In all principal analyses, subjects will be included in the group

to which they were initially assigned and this assignment will not be altered based on a subject's adherence to the assigned treatment program. Analyses of each outcome will include an assessment of possible differences among clinical centers. Baseline variables that will be used in stratified analyses include gender, HLA risk category and other prognostic characteristics. If differences in baseline characteristics are observed, analyses will be conducted of the effects of the treatments on outcomes adjusting for the potential confounding effects of these baseline characteristics. If only a few such baseline characteristics are identified, analyses will be conducted stratifying for those characteristics. If any more than a few baseline characteristics are identified, because of small sample size, it will be necessary that regression models be employed to adjust the treatment comparison for the confounding effects of those characteristics. A number of subgroup analyses are planned to help identify individuals more likely to benefit from, or to be harmed by, the treatment. In regard to treatment effects, definition of such subgroups will rely on baseline data, not data measured after randomization. Such subgroups might include: gender, gender of the relative with type 1 diabetes, HLA risk group and other factors suspected to be associated with the event. Exploratory data derived through subgroup analyses will serve primarily to generate new hypotheses for subsequent testing, and conclusions drawn from subgroup hypotheses not explicitly stated before data analysis will have less credibility than those from hypotheses stated in the protocol. For safety monitoring, the Data Management Unit also will perform any and all analyses that are appropriate to identify subgroups that may be at significantly increased safety risk. The Kaplan-Meier method will be used to construct survival curves and the logrank statistic used to compare treatment arms with respect to time until the development of autoimmunity or type 1 diabetes.

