We therefore aim to randomize 2032 infants with increased genetic risk as defined in the genetic screening section (E). To achieve that number 4516 infants must be screened assuming a frequency of 45% of the genotypes conferring increased risk. The observed prevalence of risk genotypes was 50% among the 471 infants screened for the Pilot-2 trial in Finland. An enrollment scheme for the trial proper is presented in Figure 1. This flow sheet indicates that the trial requires initial access to 5806 pregnancies. This should provide at least 4936 families with consent to participate in the trial before the birth of the child provided that the consent rate is 85%. With an exclusion rate of 8.5% after birth based on the exclusion criteria approximately 4516 infants will be available for genetic screening. The observed exclusion rate in the Pilot-2 trial was 8.6%.

Infants will be recruited over a four-year period and the planned follow-up will be 6 years after the last infant has been accrued for the antibody endpoint and 10 years after the last infant is accrued for the type 1 diabetes end point. Thus, all subjects will have at least 10 years of follow-up.

Figure 1. Enrollment scheme for TRIGR

C. RECRUITMENT

Recruitment is carried out in six major centers in USA, in 18 centers in Canada, in 12 European countries, and three centers in N.S.W., Australia. A list of participating countries and recruitment estimates are presented in Appendix 1. The figures represent an estimate of eligible pregnant women available in each country. The background of these estimates is that the appraisal of the acceptance rate (best scenario 70-80%, average 60%) may vary from country to country, and accordingly the total recruitment figures are a rough estimate. According to the figures given in Appendix 1 about 65% of the participants will be recruited in North America and 35% in Europe + Australia. The recruitment will be continued past the initial 4-year period, if we have not obtained 2,032 newborn infants with increased genetic risk to the series by that time.

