The Nutrition Epidemiology Unit ([name], National Institute for Health and Welfare, Helsinki, Finland) of the International Coordinating Center is responsible for the education and supervision concerning the assessment and maintenance of the dietary compliance and the dietary advice given by the centers involved. A continuous quality control system is implemented in each center for the data collection and content, especially to ensure that the delivery of dietary advice and the measurement of dietary compliance function properly. A specially trained Study Monitor supervises the implementation of these measures. A Nutrition Fellow at the Nutrition Epidemiology Unit oversees the dietary intervention closely supervised by [name], by means of data collected, reports from the monitors, and continuous contacts with the Study Centers.

H. STUDY ASSESSMENTS

Baseline

After the delivery medical and perinatal history of the infant and mother (including birth weight and gestational age) and the results of the newborn physical examination are recorded on the case report forms.

Follow-up Period during and after Intervention

The subjects visit the research center or have a home visit at the age of 3, 6, 9, 12, 18 and 24 months, and at 3, 4, 5, 6, 7, 8, 9 and 10 years of age, or when clinical diabetes develops.

Protocol change in 2011: The follow-up of the subjects will be continued until the youngest participant reaches the age of 10 years. The oldest participants will then be 14-year old. During the prolonged follow-up period the follow-visits will take place annually at the ages of 11, 12, 13 and 14 years. The presence or absence of diabetes is determined according to the criteria outlined below (see Outcome Assessment, below). Clinical findings at each visit (e.g. weight, height) are recorded on the case report forms.

Protocol Change in 2015: Puberty will be assessed based on hormonal analyses. Serum estradiol will be analyzed in girls and serum testosterone in boys starting from the age of 8 years. In addition girls will be asked about their age at menarche and the use of medication containing estrogens and/or androgens starting from the age of 10 years.

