	0 mo*	½, 1, 2 mo Call	3 mo Visit	4, 5 mo Call	6 mo Visit	7 mo Call	8 mo Call	9 mo Visit	12 mo Visit	18 mo Visit	2 yr Visit	3 yr Visit	4 yr Visit	5 yr Visit	6 yr Visit	7 yr Visit	8 yr Visit	9 yr Visit	10 yr Visit	11 - 14yr Visit
Contact number	1	2-4	5	6-7	8	8B	8C	9	10	11	12	13	14	15	16	17	18	19	20	21-24
Weight and height	X		X		X			X	X	X	X	X	X	X	X	X	X	X	X	X
Blood Specimens																				
- Cord blood	X																			
- Venous blood			X		X			X	X	X	X	X	X	X	X	X	X	X	X	X
- Heparin blood			X		X			X	X	X	X	X	X	X	X	X	X	X	X	X
- Blood glucose									X	X	X	X	X	X	X	X	X	X	X	X
- HbA1c									X	X	X	X	X	X	X	X	X	X	X	X
- EDTA blood														X***	X***	X***	X***	X***	X***	X***
Dietary Interview	X	X	X	X	X	X	X	X												
Dietary counselling	X	X	X	X	X	X	X													
Delivery of Study Formula	X	+ When	needed																	
Examination by Study Doctor	X		X		X				X		X				X				X	X**
OGTT															X				X	X**

* Contact number 1 takes place in the delivery hospital but in case of home deliveries it is arranged at home

** OGTT and examination by the Study Doctor will be performed in all study subjects at the last follow-up visit in 2016-2017.

*** An EDTA blood sample, 4 ml, for DNA extraction will be collected from all study participants once at the age of 5 years or later

Outcome Assessment

The major outcome for the first phase will be the frequency of type 1 diabetes-associated autoantibodies and/or the development of clinical diabetes by the age of 6 years. The outcome of the second phase will be the manifestation of diabetes by the age of 10 years. The manifest diabetes outcome is assessed as the proportion of subjects in each group who develop type 1 diabetes, as well as age at diagnosis. These subjects will be classified as having type 1 diabetes if they fulfill one of the following criteria:

- 1) Symptoms + a single random plasma glucose ≥ 11.1 mmol/l = 200 mg/dl (venous blood glucose > 10.0 mmol/l = 180 mg/dl)
- 2) If the child has no symptoms the diagnosis requires
 - a) A raised random plasma glucose reading ≥ 11.1 mmol/l = 200 mg/dl (venous blood glucose ≥ 10.0 mmol/l = 180 mg/dl) on two occasions or
 - b) A raised fasting plasma glucose readings ≥ 7.0 mmol/l = 126 mg/dl (venous blood glucose ≥ 6.1 mmol/l = 110 mg/dl) on two occasions or
 - c) A diabetic oral glucose tolerance test by WHO criteria
 - fasting venous plasma glucose ≥ 7.0 mmol/l = 126 mg/dl (fasting venous blood glucose ≥ 6.1 mmol/l = 110 mg/dl) on two occasions
or

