It is critical to ensure that subjects who are randomized to receive the intervention formula, are not exposed to CM protein during the intervention period. The risk is especially high in the immediate postpartum period when a newborn infant may be given the wrong formula for supplementation in the hospital nursery. To prevent such contamination, infants who are in the study are clearly identified to all nursery personnel. Any formula supplementation for these infants is only with Nutramigen if formula is required prior to randomization (interim formula).

K. DATA BASE

The database is held at the Pediatrics Epidemiology Center at the University of South Florida, Tampa, FL, headed by [name]. The web sites were built by the DMU in Tampa with the assistance of the TRIGR International Coordination Center in Helsinki. The DMU has established the data transfer system between the laboratories and the database using File Transfer Protocol (FTP) technique. The system has recently been tested. The DMU created a password-based security management system for all the users who are authorized in the system and the user information was collected and saved in the system.

L. STATISTICAL METHODS

A two part hypotheses will be tested. The first hypothesis is that the children in the group fed casein hydrolysate will have a decreased occurrence of diabetes-associated antibodies in comparison with the control group receiving conventional CM-based formula. The second hypothesis is that the group weaned to a casein hydrolysate formula has a reduced incidence of type 1 diabetes.

The first hypothesis will be studied based on a longitudinal data set consisting of repeated measurements of several variables at standard time points. The variables measured at these time points are potential confounding factors (i.e., factors the effects of which have not fully been eliminated by the randomization), effect modifying factors (such as possible occurrence of differences in weight and height development, which may have the ability to modify the effect of the CM exposure considered)

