and the outcome variables (e.g., the status of the diabetes-associated antibodies). At every time point the single antibody variable will be dichotomized as negative or positive, and a summary variable will be produced (negative if less than two variables are antibody positive and positive if two or more variables are antibody positive). The exposure to formula vs. placebo will be included in the model as an indicator variable. Age at initiation, duration of breast feeding and/or formula use and cumulative formula dose will be included in the model as potential effect modifying and confounding factors. The presence of interactions will be tested and the possible effect of the components considered will be estimated.

Two different statistical methods will be used to analyze the hypothesis that weaning to a casein hydrolysate decreases the occurrence of diabetes-associated antibodies. First, generalized linear models will be fitted to the data (20). Also random effect models will be used (21). These models which represent a general approach to the problem of modeling repeated measurements with fairly general error structures, can allow for missing observations, serial correlations, time-varying covariates, and irregular measurement occasions. Second, for the description of the data, the association of covariates with the risk of an elevated antibody at a given point of time will be assessed using logistic regression models (22). A rather similar statistical approach was used in the DCCT Study (23).

The analyses of the second hypothesis will use the time of diagnosis of manifest type 1 diabetes as the only outcome measure. The dataset will thus be similar to that of a cohort study, and the statistical analyses will be carried out using the proportional hazards regression model (24) including the milk exposure as the risk factor and potential confounding factors a covariates in the model. Also time-dependent covariates can be included to assess the effects of potential modifying factors. The adjusted relative risk of type 1 diabetes between the two groups of milk exposure will be estimated. Also the adjusted incidence of the disease in the two groups can be assessed.

M. INTERIM ANALYSIS

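### No single primary test is named for the phase-1 outcome (autoantibodies and/or diabetes by age 6): Sections B, H and L give different endpoints, methods and horizons

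*Combined protocol and SAP*

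**What the plan says.** Four places bear on the first-phase analysis.

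- **Section H, Outcome Assessment.** The major first-phase outcome is "the frequency of type 1 diabetes-associated autoantibodies and/or the development of clinical diabetes by the age of 6 years".
- **Section L.** "The first hypothesis will be studied based on a longitudinal data set consisting of repeated measurements of several variables at standard time points". The outcome variable is defined as follows: "At every time point the single antibody variable will be dichotomized as negative or positive, and a summary variable will be produced", counted positive when two or more antibodies are positive. The methods are generalized linear models and random-effect models, plus logistic regression at single time points, which is labelled descriptive. Diabetes appears only under the second hypothesis, where it is the sole outcome, analysed by proportional hazards.
- **Section B, analysis paragraph after Table 1.** Kaplan-Meier curves are planned, with "the logrank statistic used to compare treatment arms with respect to time until the development of autoimmunity or type 1 diabetes". Autoimmunity is not defined. Table 1 is headed "Reduction in the annual frequency of multiple auto-antibodies (≥ 2 AB) by the age of 6 years", which suggests two or more antibodies. The text before it, however, quotes both counts: "expected cumulative incidence of at least one antibody would be 14.8% and that of at least two antibodies 13.0" per cent by age 6.
- **Section B, follow-up paragraph.** Recruitment takes four years and "the planned follow-up will be 6 years after the last infant has been accrued for the antibody endpoint".

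Section M lets the monitoring board look repeatedly at autoantibodies and at clinical diabetes, and a sufficiently significant result on either opens the code and is published. It does not name the test. The phrase *principal analyses* occurs once, in Section B, and concerns only keeping children in their assigned group.

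**The concern.** The stated outcome asks whether a child has had the event by age 6. Section L's first-hypothesis models ask how often visits are antibody-positive, over an unstated age range. Section B's log-rank test asks when the first event occurred. The first-phase claim could rest on either analysis, over either horizon, and nothing in the plan prevents the choice from being made after results by arm are known.

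Diabetes matters to the definition because visits are scheduled "and at 3, 4, 5, 6, 7, 8, 9 and 10 years of age, or when clinical diabetes develops". A child diagnosed between visits, before any positive sample, is an event under Section H but may never be one under Section L's first hypothesis. The interim antibody look raises the stakes, because an unnamed test could open the code.

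**Working it through.** **1. What Table 1's antibody row assumes.** Inputs from Section B: 9.9% with two or more antibodies by age 6 (lowest row), 40% effect, 95% confidence, 80% power, four-year accrual, and follow-up until six years after the last infant. Assumptions: two-sided test, equal allocation, constant hazards.

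- Events (Freedman): (1.960 + 0.8416)² × ((1 + 0.6)/(1 − 0.6))² = 7.849 × 16 = 125.58.
- Control hazard: −ln(1 − 0.099)/6 = 0.017375 per year. Treated: 0.6 × 0.017375 = 0.010425.
- Follow-up uniform over 6–10 years: event probability = 1 − (e^(−6λ) − e^(−10λ))/(4λ), which gives 0.1296 and 0.0800, mean 0.10477. N = 125.58/0.10477 = **1199**. Table 1 states **1200**.
- Cut at age 6: 0.099 and 1 − 0.901^0.6 = 0.0606, mean 0.07982. N = 125.58/0.07982 = **1573**.

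So the sizing fits a time-to-event comparison over ages 6–10, although the table heading and Section H both say by age 6.

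**2. How much the choice of test matters.** Simulation with constant seroconversion hazard 0.01738 and progression hazard 0.142 per year. The latter is solved so that control diabetes by age 10 is 7.6%, Table 1's lowest diabetes row. The antibody hazard is 40% lower under treatment, antibodies persist once present, and visits follow Section H. The visit model is a GEE with visit terms and a robust score test. Size is 2032/2 = 1,016 per arm, with data to age 6. Ranges span repeat runs and whether a sample is taken at diagnosis.

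| Analysis | Power | Verdict differs from log-rank |
|---|---|---|
| Log-rank, antibodies or diabetes | 87–89% | – |
| GEE, independence | 73–77% | 15–19% |
| GEE, AR(1) | 83–86% | 5–7% |

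Compared within runs, the log-rank advantage is about 12–15 points over independence. Over AR(1) it is about 2–5 points, allowing for simulation error.

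**3. Type I error from taking either test.** Under the null, the log-rank and independence-GEE statistics correlate at about 0.81, so the chance that at least one is significant at 5% is 7.7% (bivariate normal). With AR(1) the correlation is 0.94–0.97 and the figure 6.0–6.7%. Overall this is about 6–8%.

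**4. What the diabetes component adds.** Expected events: 1,016 × 0.099 + 1,016 × 0.0606 = 100.6 + 61.6 = 162. About 9 are children diagnosed before a positive visit sample. Log-rank power is 89% with them and 87% on antibodies alone, so the case for including them is fidelity to the stated outcome more than power.

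**5. Sensitivity.**
- *Higher Table 1 rows* (18.5%/15.4% and 20.7%/18.3%): log-rank 98–99.7% against 89–97% for the independence GEE.
- *Drop-outs removed entirely* (1,016 × 0.8 = 813 per arm), lowest row: log-rank 82%, independence 65–68%, AR(1) 77–79%. This is pessimistic. Table 1's antibody row charges only 1300/1200 = 1.083, about 8%, for the same drop-out, and Section B keeps all available data.
- *Follow-up to ages 6–10*, lowest row, 1,016 per arm: log-rank 96%, independence GEE 84–86%.

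Random-effect models were not simulated.

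**The case against.** **Section H's *and/or* may mean two endpoints.** Section L opens with a two-part hypothesis, and Section M speaks of separate antibody and diabetes analyses. On that reading Section L covers each component. This is a fair reading, but the age-6 horizon and the ranking would still be missing.

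**The plan already has the composite test.** A reader might infer that no planned analysis addresses the Section H outcome. That goes too far: Section B's log-rank test comes close. What is missing is a definition of autoimmunity, an age limit, and a statement of where this test stands relative to Section L.

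**Section L is the methods section and implies a hierarchy.** It does mark the logistic models as descriptive. That orders methods within Section L only and does not place the log-rank test.

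**The power gap is a modelling choice.** This largely stands. Section L does not specify an independence working correlation, and it favours models that accommodate serial correlation. With AR(1) most of the gap disappears.

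**The change comes late.** This version is dated April 2015 and last visits fall in 2016–2017, when the youngest child reaches 10, so every child is already past 6. Section O's timetable opens the code in year 16, so on that schedule the choice can still precede unblinding. It can govern only interim looks not yet made.

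**Conclusion.** The concern holds as a conflict of text: the outcome definition, the Section L models, the Section B log-rank test and the antibody follow-up period do not describe one analysis, and nothing names the primary one. This conclusion does not depend on simulation.

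The size is moderate and model-dependent. At the lowest Table 1 rates, 1,016 per arm and data to age 6, the log-rank advantage is about 12–15 points against an independence GEE and about 2–5 against AR(1). Verdicts differ in about 15–19% and 5–7% of trials, and a free choice between tests takes type I error from 5% to about 6–8%. These figures rest on constant hazards, persistent antibodies and a 40% lower seroconversion hazard.

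A reader might infer that Section L's models are clearly weaker. The documents do not support that as a general statement, because they leave the correlation structure open and also name random-effect models, which were not evaluated. Nor do these results show how a rule for maternally acquired antibody in early samples would affect power, since no maternal antibody was simulated. The second-phase analysis of time to diabetes is unaffected.

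**What to change.** Before unblinding, amend the SAP wording as follows.

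1. Name one primary phase-1 analysis: Section B's log-rank/Cox comparison of time to the first confirmed sample with two or more autoantibodies, or diagnosis of type 1 diabetes, whichever comes first, by age 6. Confirmed means after the retests already described in Section I.
2. Define autoimmunity in Section B in the same way.
3. Use this test for any remaining antibody look under Section M.
4. Keep Section L's longitudinal models, and antibody data after age 6, as supportive analyses, and state the correlation structure.

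The gain is one pre-named test that counts children diagnosed before a positive sample. It needs no added visits, samples or assays.

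There are two costs. The repeated-measures models become secondary. The age-6 limit also moves follow-up that Table 1's antibody sizing appears to use into a supportive role: log-rank power at the lowest row and 1,016 per arm falls from about 96% to 89%, still above the 80% target.
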